5.3 Treatment Assignment Procedures

5.3.1 Randomization Procedures

Volunteers will not be randomized to study treatment. All eligible volunteers will receive either quadrivalent live, attenuated influenza vaccine (LAIV4) or quadrivalent inactivated influenza vaccine (IIV4) based upon eligibility and group assigned.

5.3.2 Reasons for Withdrawal

A study participant will not receive the study product at the first visit if a significant intercurrent illness, or other medical condition or situation occurs that meets the exclusion criteria. Volunteers will be withdrawn from the study if participation in the study would not be in the best interest of the participant, or if doing so would harm the participant in the opinion of the investigator. Participants may withdraw from the study voluntarily.

5.3.3 Handling of Withdrawals

If, for safety reasons a participant is deemed by the investigators to not be eligible to receive the study product as per protocol, he/she will be terminated from the study. If a participant voluntarily withdraws from the study or is withdrawn by the investigator after immunization, the participant will be followed for safety whenever possible until Day 28 post-immunization or until any serious adverse events are resolved or considered stable.

5.3.4 Termination of Study

The study may be terminated for administrative reasons or other unanticipated circumstances.

6 STUDY INTERVENTION/INVESTIGATIONAL PRODUCT

6.1 Study Product Description

6.1.1 Acquisition

The study product will be shipped from the manufacturer to the investigational pharmacy at the study site. The quadrivalent IIV4 will be supplied by Sanofi-Pasteur as Fluzone® Quadrivalent. The LAIV4 will be supplied by MedImmune as FluMist® Intranasal spray, Quadrivalent Influenza Vaccine.

6.1.2 Formulation, Packaging, and Labeling

FDA's Vaccines and Related Biological Products Advisory Committee (VRBPAC) will make annual recommendations regarding the composition of the U.S. seasonal influenza vaccines based on global influenza virus surveillance data related to epidemiology and antigenic characteristics, serological responses to trivalent and quadrivalent seasonal vaccines, and the availability of candidate strains and reagents.

The season-specific manufacturer package inserts for each study year will be attached in the IRB protocol submissions when available.

Fluzone® Quadrivalent: Each 0.5 mL dose of Fluzone Quadrivalent (IIV4) will contain a total of 60 µg (15 µg of each strain) of influenza virus hemagglutinin of each of the 4 strains selected for the seasonal formulation. Each 0.25 mL dose contains a total of 30 µg (7.5 µg of each strain). The vaccine will be supplied in a prefilled, single dose syringe 0.25 mL (no preservative) 0.5 mL (no preservative), single dose vial 0.5 mL (no preservative) or multi-dose vial, 5 mL (with preservative). Each multi-dose vial contains ten 0.5 mL doses.

FluMist® (Influenza Virus Vaccine) Live, Intranasal Spray.

Each pre-filled refrigerated FluMist® Quadrivalent sprayer contains a single 0.2 mL dose. Each 0.2 mL dose contains $10^{6.5-7.5}$ FFU (fluorescent focus units) of live attenuated influenza virus reassortants of each of the selected strains. Each 0.2 mL dose may also contains 0.188 mg/dose monosodium glutamate, 2.00 mg/dose hydrolyzed porcine gelatin, 2.42 mg/dose arginine, 13.68 mg/dose sucrose, 2.26 mg/dose dibasic potassium phosphate, and 0.96 mg/dose monobasic potassium phosphate. Each dose contains residual amounts of ovalbumin (< 0.24 mcg/dose), and may also contain residual amounts of gentamicin sulfate (< 0.015 mcg/mL), and ethylenediaminetetraacetic acid (EDTA) (< 0.37 mcg/dose). FluMist® Quadrivalent contains no preservatives. It is supplied in a package of 10 pre-filled, single-dose (0.2 mL) intranasal sprayers.

6.1.3 Product Storage and Stability

Fluzone® Quadrivalent vaccine presentations should be refrigerated at 2° to 8°C (35° to 46°F). Vaccine that has been frozen will be discarded. Between uses, multi-dose vials will be returned to the recommended storage conditions at 2° to 8°C (35° to 46°F). Should not use after the expiration date shown on the label.

FluMist® Quadrivalent should be stored in a refrigerator between 2 to 8°C (35-46°F) upon receipt and until use. The product must be used before the expiration date on the sprayer label and must not be frozen. The cold chain (2 to 8°C) must be maintained when transporting FluMist® Quadrivalent. Once FluMist® Quadrivalent has been administered; the sprayer should be disposed of according to the standard procedures for medical waste (e.g., sharps container or biohazard container). One should not use after the expiration date shown on the label.

6.2 Dosage, Preparation and Administration of Study Intervention/Investigational Product

Fluzone® Quadrivalent: 0.25 mL for children 6 months to 35 months of age and 0.5 mL for 36 months – adults. IIV4 vaccine will be administered with a sterile, disposable syringe and needle by IM injection into the thigh or deltoid muscle. The participant/clinician will choose whether the injection will be administered into the thigh or right or left deltoid. Previously unvaccinated children through 8 years of age should receive two doses of influenza vaccine - one on day 0, followed by a second dose at least 28 days later.

LAIV4 vaccine dosage is 0.2 mL. Vaccine will be administered as an intranasal spray. Each sprayer contains a single dose of FluMist® Quadrivalent; approximately one-half of the contents should be administered into each nostril. 0.1 mL (i.e., half of the dose from a single FluMist sprayer) is administered into each nostril while the recipient is in an upright position. Insert the tip of the sprayer just inside the nose and rapidly depress the plunger until the dose-divider clip stops the plunger. The dose divider clip is removed from the sprayer to administer the second half of the dose (0.1 mL) into the other nostril. Previously unvaccinated children through 8 years of age should receive two doses of influenza vaccine - one on day 0, followed by a second dose at least 28 days later.

6.3 Accountability Procedures for the Study Intervention/Investigational Product(s)

The study article will be shipped by the manufacturer to the investigational pharmacy at the study site. Use and disposition of each unit of vaccine will be appropriately documented by the Clinical Core staff in accordance with ICH GCP. Unused products will be returned to the investigational pharmacy for use or destruction.

6.4 Concomitant Medications

At each study visit, the participant will be questioned about any vaccinations they have received or concomitant medication use, and the information will be recorded. Medication history will include medications taken within 28 days prior to enrollment and currently taken prescription and over-the-counter medications used throughout the study period. The investigator should be consulted regarding eligibility if the participant is taking oral steroid medications or medications for treatment of autoimmune disease (such as Plaquenil, methotrexate, prednisone, Enbrel), anti-coagulation/anti-platelet medications such as Coumadin, Lovenox, aspirin (except aspirin up to 325 mg. per day), Plavix, Aggrenox, or any other medications which might indicate a condition that precludes participant compliance with the protocol.

7 STUDY SCHEDULE

7.1 Screening

Volunteers will be contacted by phone prior to the first study visit. Study staff will briefly review the eligibility criteria, participant availability and the study procedures. If the participant is eligible and interested, the volunteers will be assigned to groups based on, age, inclusion exclusion criteria and availability for annual return vs single year participation.

7.2 Day 0; Enrollment/Baseline/Immunization for all Groups; annually for Groups A and D.

- Adult participants or parents of the volunteer will be provided with a verbal description of the study (purpose and study schedule and procedures). They then will be asked for any questions and to read/sign the consent form (in the first year only). Minor children ages 7-17 years will be given an assent at enrollment. The consent form will be signed prior to the performance of any study procedures. The study staff will discuss with the volunteer or volunteer's parent of their study eligibility criteria and concomitant medication use.
- Obtain vital signs (oral temperature, pulse, and respiratory rate), height and weight. Obtain blood pressure for volunteers 12 years and older.
- Collect blood samples (**except Group C**) as follows:

For blood volumes ≥ 20 mL, collect one 5 mL gold top tube (serum), one 2.5 mL PAXgene tube and one 2.5 mL heparinized, green top tube (CyTOF sample). The remainder of the blood sample will be collected in heparinized, green top tubes. Blood volumes <20 mL will be collected in heparinized, green top tubes only.

- For children weighing more than 100 lb., and from adults, total volume not to exceed 70 mL
 - From children weighing 66-100 lb: total volume not to exceed 30 mL
 - From children weighing 61-65 lb: total volume not to exceed 25 mL
 - From children weighing 41-60 lbs: total volume not to exceed 20 mL
 - From children weighing 16-40 lbs: total volume not to exceed 10 mL
 - From children 6 months through 35 months old, regardless of weight: Obtain a 4 mL blood sample into a heparin (green top) tube.
- All volunteers will be administered the seasonal flu vaccine according to the group assignment. Unless there is a different recommendation from the ACIP in a given year, Group A, B, C and F will receive intranasal spray of LAIV4. Group D, E and G

will be vaccinated with IIV4. Children who are vaccine-naïve will receive their Dose 1 of their vaccine at this visit. Volunteers will be observed in clinic for 15 minutes for any immediate serious reactions. Vaccine-naïve volunteers requiring Dose 2 will return at least 28 days post-Dose 1.

- A Memory Aid will be given to the volunteers/volunteer's parent with written and oral instructions for collection of information about serious adverse events. The memory aid is a simple diary for volunteer to record change in a health status and medications between study visits.
- The schedule for subsequent study visits will be reviewed.

7.3 Day 1 post- Dose 1 immunization for Group C and Group F only

- Review of medications and memory aid for serious adverse events
- Collect nasopharyngeal swab specimen; no blood sample will be collected at this visit.
- The schedule for subsequent study visits will be reviewed.

7.4 Day 6-8 post-Dose 1 immunization except Group C and vaccine-naïve volunteers in Group D and Group E requiring Dose 2; annually for Groups A and D.

- Review of medications and memory aid for serious adverse events
- Collect blood samples as follows:

All blood samples will be collected in heparinized, green top tubes to be picked up by the [name] lab for processing and analysis. For sample volumes >30 mL, one heparinized, green top tube will be sent to the HIMC if available ([name] lab requires at least 30 mL in heparinized, green top tubes at Day 6-8).

- For children weighing more than 100 lb., and from adults: total volume not to exceed 70 mL
 - From children weighing 66-100 lb: total volume not to exceed 30 mL
 - From children weighing 61-65 lb: total volume not to exceed 25 mL
 - From children weighing 41-60 lbs: total volume not to exceed 20 mL
 - From children weighing 16-40 lbs: total volume not to exceed 10 mL
 - From children 6 months through 35 months old, regardless of weight: Obtain a 4 mL blood sample into a heparin (green top) tube.
- The schedule for subsequent study visits will be reviewed for, Group F and G

- This will be the final visit for volunteers with prior influenza vaccination history in Group A, B, D and E. Complete Study Status form and Study Reimbursement form for these volunteers.

7.5 Day 21 post-Dose 1 immunization for Group C only

- Review of medications and memory aid for serious adverse events
- Collect nasopharyngeal swab specimen.
- No blood sample will be collected at this visit.
- This will be the final visit for volunteers with prior influenza vaccination history. Complete Study Status form and Study Reimbursement form for these volunteers.

7.6 Day 28 post-Dose 1 immunization

7.6.1 Day 28-32 for vaccine-naïve volunteers requiring second dose of vaccine (Groups A, B, C, D and E)

- Review of medications and memory aid for serious adverse events
- Obtain temperature.
- No blood samples will be collected at this visit
- Volunteers will be vaccinated with the same type of vaccine as Dose 1 and observed in clinic for at least 15 minutes for any immediate serious adverse events.
- Complete Study Status form and Study Reimbursement form for Groups A, B and C.
- For Groups D and E Memory aid will be given with written and oral instructions for collection of information about serious adverse events.
- The schedule for subsequent study visit will be reviewed for Group D and E

7.6.2 Day 28 ± 4 for Groups F and G

- Review of medications and memory aid for serious adverse events
- Collect nasopharyngeal swab specimen for Group F only
- Collect blood samples for both group as follows:

For blood volumes ≥ 20 mL, collect one 5 mL gold top tube (serum). The remainder of the blood sample will be collected in heparinized, green top tubes. Blood volumes

<20 mL will be collected in heparinized, green top tubes only.

- For children weighing more than 100 lb., and from adults, Volume not to exceed 70 mL
 - From children weighing 66-100 lb., total volume not to exceed 30 mL
 - From children weighing 61-65 lb., total volume not to exceed 25 mL
 - From children 6 months through 35 months old, regardless of weight: Obtain a 4 mL blood sample into a heparin (green top) tube.
- Complete Study Status form and Study Reimbursement form

7.7 Day 6-8 post-Dose 2 immunization for previously vaccine-naïve volunteers in Group D and E

- Review of medications and memory aid for serious adverse events
- Collect blood samples for both group as follows:

All blood samples will be collected in heparinized, green top tubes to be picked up by the [name] lab for processing.

- From children weighing 41-60 lbs. total volume not to exceed 20 mL
 - From children weighing 16-40 lbs. total volume not to exceed 10 mL
 - From children 6 months through 35 months old, regardless of weight: Obtain a 4 mL blood sample into a heparin (green top) tube.
- Complete Study Status form and Study Reimbursement form

7.8 Early Termination Visit

If a volunteer is terminated from the study early, every effort should be made to perform the following procedures:

- Review current health status and note any changes since the last visit. Solicit information regarding SAEs and record all concomitant medications. Any ongoing related SAEs will be followed to resolution or until a stable chronic condition has been established. Volunteers will be encouraged to permit continued follow-up of SAEs if necessary
- Obtain remaining samples, if possible.

8 STUDY PROCEDURES/EVALUATIONS

8.1 Clinical Evaluations

Clinical Evaluation will be obtained by interview with a research nurse, and will include:

- Review eligibility and past medical history including influenza vaccine history.
- Medication history of medications used within 28 days prior to enrollment and currently taken prescription and over-the-counter medications used throughout the study period.
- Height, weight, temperature, pulse, BP on adolescents and adults.
- Review of memory aid for serious adverse events occurring during the 28 day study period.

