Stanford U19 CCHI. Project 2: Innate and Acquired Immunity to Influenza Infection and Immunization (Under grant 'Adaptive and Innate Immunity, Memory and Repertoire in Vaccination and Infection'); SLVP029.
V2.0_07AUG2015

OHSR	Office for Human Subjects Research
ORA	Office of Regulatory Affairs, DMID, NIAID, NIH, DHHS
PHI	Protected Health Information
PI	Principal Investigator
PK	Pharmacokinetics
QA	Quality Assurance
QC	Quality Control
SAE	Serious Adverse Event/Serious Adverse Experience
SLVP	Stanford-LPCH Vaccine Program
SMC	Safety Monitoring Committee
SOP	Standard Operating Procedure
TIV	Trivalent inactivated influenza vaccine
US	United States
WHO	World Health Organization

PROTOCOL SUMMARY

Title: Project 2: Innate and Acquired Immunity to Influenza Infection and Immunization	
Number of Sites: 1	
Study Duration: 5 years for enrollment, vaccination, analysis	
Subject Participation Duration: 4-5 weeks	
Description of Agent or Intervention: Quadrivalent, Live Attenuated Influenza Vaccine (LAIV4) Quadrivalent, Inactivated Influenza Vaccine (IIV4)	
Objectives:	
Primary:
 
 1. To compare the nasal mucosal transcriptional responses to LAIV4 between the following age groups: 2-4 year old children, 9-13 year old children, and 18-49 year old adults 2. To compare the B cell response to LAIV4 between the following age groups: 2-4 year old children, 9-13 year old children, and 18-49 year old adults 3. To investigate the evolution of B cell repertoire in young children after repeated LAIV4 immunization 4. To compare the B cell response to IIV between the following age groups: 6-23 month old children, 9-13 year old children, and 18-49 year old adults 5. To investigate the evolution of B cell repertoire in young children first immunized with IIV followed by repeated LAIV4 immunization. 
Secondary:
 
 1. To compare the B cell repertoire in response to LAIV4 versus IIV in different age groups.

Description of Study Design: This is a Phase IV study of healthy children and adults who will receive the current seasonal influenza vaccine. There are no exclusions for gender, ethnicity or race. The volunteers will be enrolled into one of 7 groups over a 5-year period. Immunization will be at Day 0. Blood and NP swab samples will be collected at various time points based upon group assignment for various immunological assays.

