response than LAIV in adults and older children, but one year after vaccination with either LAIV or IIV the levels of flu-specific circulating memory B cells are similar²⁶. This indicates that convalescent serum Ab titers do not give a complete picture of B cell mediated immunity following vaccination.²⁶⁻³² and infection^{30, 33-34}. We and others have studied the B cell response to flu vaccination by examining the acute circulating plasmablast (PB) response. Analysis of this response provides a snapshot of the overall B cell response to recent Ag exposure without the confounding effects of preexisting circulating Abs. Analysis of the PB Ab repertoires revealed that the B cell response of adults to flu vaccination is largely a recall response of pre-existing memory B cells²⁸. In preliminary studies, we identified flu-specific PBs that recognized previously circulated flu viruses better than current vaccine strains. These observations suggest that both the quantitative and qualitative nature of the B cell response to a new flu vaccination or to infection in the flu-experienced individuals is fundamentally shaped by the pre-vaccination memory B cell repertoire. However, factors that initially establish this repertoire and the evolution of this repertoire during repeated exposure to influenza antigens, especially during repeated immunization with different types of influenza vaccines, the mechanism of its regulation, and the impact of initial Ag exposure on subsequent flu immunity in different age groups are unknown.

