3 OBJECTIVES

3.1 Study Objectives

Primary:

1. To measure the nasal mucosal transcriptional responses to LAIV4 in the following age groups: 2-4 year old children, 9-13 year old children, and 18-49 year old adults.
2. To measure the B cell response to LAIV4 in the following age groups: 2-4 year old children, 9-13 year old children, and 18-49 year old adults.
3. To measure the B cell response to IIV4 in the following age groups: 6 month-4 year old children, 9-13 year old children, and 18-49 year old adults.

Secondary:

1. To compare the nasal mucosal transcriptional responses to LAIV4 between the different age groups.
2. To determine the evolution of B cell repertoire in young children after repeated immunization with different types of influenza vaccines.
3. To compare the B cell repertoire in response to LAIV4 versus IIV4 in different age groups.

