4 STUDY DESIGN

This is a Phase IV study of healthy children and adults who will receive the current seasonal influenza vaccine. There are no exclusions for gender, ethnicity or race. The volunteers will be enrolled into one of 7 groups over a 5 year period. Following confirmation of written informed consent and assent, immunization will be administered; blood samples and NP swabs for immunogenicity assays will be collected at various time points based on groups assigned. All volunteers will be followed for serious adverse events (SAEs).

Group A (LAIV4/annual return): Up to six 2-4 year old volunteers will be given a quadrivalent live, attenuated influenza vaccine (LAIV4). Blood samples to conduct the assays described will be taken at Day 0 pre-immunization and Day 6-8 post-Dose 1 for all children irrespective of those who require 1 dose (prior flu vaccination history) or 2 doses (vaccine-naïve). For children requiring 2 doses of vaccine, a second immunization will be given at Day 28-32 after Dose 1. All participants in this group will be asked to return annually for flu immunization and blood samples.

Group B (LAIV4/ single year): Up to twenty 2-4 year old volunteers will be given a quadrivalent live, attenuated influenza vaccine (LAIV4). Blood samples to conduct the assays described will be taken at Day 0 pre-immunization and Day 6-8 post-Dose 1 for all children irrespective of those who require 1 dose (prior flu vaccination history) or 2 doses (vaccine-naïve). For children requiring 2 doses of vaccine, a second immunization will be given at Day 28-32 after Dose 1.

Group C (LAIV4/NP swab group): Up to twenty 2-4 year old volunteers will be given a quadrivalent live, attenuated influenza vaccine (LAIV4). NP swabs will be collected at Day 1 and Day 21 post-Dose 1 for all children irrespective of those who require 1 dose or 2 doses of vaccine. For children requiring 2 doses of vaccine, a second immunization will be given at Day 28-32 after Dose 1. No blood will be collected for this group.

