10 STATISTICAL CONSIDERATIONS

10.1 Study Hypotheses

1. Infection of the URT with LAIV4 or wt virus triggers hierarchical transcriptional signatures in local resident epithelial and immune cells that regulate viral replication and subsequent immunity.

2. The antigen-specific Ig repertoires elicited by IIV4 are quantitatively and qualitatively distinct, especially in young children undergoing the first or second exposure to flu antigens, and are different from those in flu-experienced adults in terms of number, size, Ig gene usage, and isotype of clonally expanded Ig gene families, and in levels of somatic hypermutation and heterovariant cross-reactive Ab activity.

This is an exploratory study aimed at providing initial estimates for subsequent studies design aimed at identifying age-specific characteristics in B cell response to influenza vaccine.

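### In Groups A and D no listed step asks about influenza illness between seasons, so year-to-year repertoire change after repeated vaccination cannot be separated from change due to natural infection.

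*Combined protocol and SAP*

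**What the plan says.** The Protocol Summary lists two of its primary objectives as "To investigate the evolution of B cell repertoire in young children after repeated LAIV4 immunization" and "To investigate the evolution of B cell repertoire in young children first immunized with IIV followed by repeated LAIV4 immunization". Section 3.1 places the same aim among the secondary objectives: "To determine the evolution of B cell repertoire in young children after repeated immunization with different types of influenza vaccines".

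Two small groups serve this aim. Section 4 describes the first as "Group A (LAIV4/annual return): Up to six 2-4 year old volunteers" and adds: "All participants in this group will be asked to return annually for flu immunization and blood samples". Group D is its counterpart, with up to six children who start on IIV4 at 6 to 23 months. Under the Appendix A footnote they move to LAIV4 at age two unless a contraindication develops. Inclusion criterion 4 (5.1) sets annual participation at up to five years.

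On health information, section 8.1 includes "Review of memory aid for serious adverse events occurring during the 28 day study period". It also lists a general past medical history that covers influenza vaccination. Section 7.2 describes the memory aid as a diary of health changes and medicines between visits, issued with instructions about serious adverse events. The Day 0 list in 7.2, repeated annually for Groups A and D, covers eligibility, concomitant medication, vital signs, blood and vaccination. Section 10.3 compares repertoire features between vaccines and age groups. It has no infection term and no longitudinal method.

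**The concern.** After each season's last study visit, a child in Group A or D is out of contact until the next Day 0. Vaccination takes place from August to December (Protocol Summary), and children with a vaccination history finish the season at Day 6-8 (7.4). Most of the following influenza season therefore falls outside observation.

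The protocol's own science makes this matter. Section 2.2 hypothesizes that wild-type infection, like LAIV4, elicits repertoires distinct from those after IIV4. Section 2.1 says that the response to a new exposure is "fundamentally shaped by the pre-vaccination memory B cell repertoire". An infection between seasons is thus a competing cause of the outcome that these groups exist to measure. With at most six children per group, one or two such infections could create or hide an apparent effect of the vaccine sequence.

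A related gap exists at entry. Section 10.1 places the expected differences "especially in young children undergoing the first or second exposure to flu antigens", but inclusion criterion 6 (5.1) defines prior exposure by vaccination alone.

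**Working it through.** **Step 1. Would any listed step reveal an ordinary influenza illness between seasons?**

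- *Annual Day 0 (7.2):* no item on influenza illness since the last visit.
- *Medical history (8.1):* general. It names influenza vaccination but not influenza illness.
- *Memory aid (7.2, 8.1):* the diary is open to any health change, but its review is directed at SAEs in a 28-day period.
- *Medication and vaccination questions (6.4, 8.1):* vaccinations received, medicines in the 28 days before enrollment, and medicines during the study period. Nothing says that an antiviral taken months before an annual return would be asked about.
- *Exclusion 20 (5.2):* influenza antivirals only in the 48 hours before vaccination.
- *NP swabs (Appendices A and B):* Groups C and F only.
- *HAI (8.2.1):* described as a measure of response to vaccination. Under 7.2 a sample below 20 mL yields no serum tube, children of 6 to 35 months give 4 mL of heparinized blood, and those of 16-40 lb give at most 10 mL. Serum is possible only for heavier children, so serology cannot be relied on to show an infection between seasons.

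An illness might come up by chance. None of these steps asks for it specifically, and none is linked to 10.3.

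**Step 2. How many children could be affected?**

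The plan has no figure to reproduce here. Section 10.2 gives 20 per age group without alpha, power or effect size, and does not address the annual groups of six.

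Inputs:
- Children per group: 6 (section 4).
- Seasons per child: at most 5 (5.1), so at most 5 - 1 = 4 between-season intervals.
- Infection risk per child per season, r: not in the documents. Assumed 10%, 20% and 30%, with 5% as a low check. Risk is taken as constant and as independent across children and years.

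Formulas:
- Expected number infected in one interval: 6r.
- Chance that a child is infected at least once in k intervals: q = 1 - (1 - r)^k. Expected number of six: 6q.
- Chance that at least one of six is infected in k intervals: 1 - (1 - r)^(6k).

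Example, r = 0.10 and k = 4: q = 1 - 0.9^4 = 1 - 0.656 = 0.344, and 6 x 0.344 = 2.06 children. The chance of at least one is 1 - 0.9^24 = 1 - 0.080 = 0.92.

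| r | Expected of 6, one interval | At least one of 6, one interval | Expected of 6, two intervals | Expected of 6, four intervals | At least one of 6, four intervals |
|---|---|---|---|---|---|
| 5% | 0.3 | 26% | 0.6 | 1.1 | 71% |
| 10% | 0.6 | 47% | 1.1 | 2.1 | 92% |
| 20% | 1.2 | 74% | 2.2 | 3.5 | 99.5% |
| 30% | 1.8 | 88% | 3.1 | 4.6 | >99.9% |

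The four-interval columns are a maximum: they need enrollment in the first season and a return in every later one. The counts cover all infections, including mild ones that a parent would not report.

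**Step 3. Which contrast is affected?**

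The annual pre-vaccination sample means that an infection before Day 0 is already reflected in that season's baseline. It does not help the year-to-year contrast, where a shift in Day 0 repertoire may come from last season's vaccine or from infection. Under the statement in 2.1, the earlier infection may also change the size or content of the next response to vaccine.

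**The case against.** The strongest reply is that the protocol does collect health information and makes no explicit causal claim.

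- *Collection.* A reader might infer that an infection that is not an SAE would leave no trace. The documents do not support that. The nurse interview in 8.1 includes past medical history, and the diary in 7.2 is wider than SAEs. What stands is that influenza is not specifically elicited, and it is unclear whether the diary covers the months between seasons.
- *Attribution.* A reader might infer that infection-driven change will be reported as a vaccine effect. No section says so. The objectives speak of evolution after repeated immunization, section 2.1 refers more broadly to repeated antigen exposure, and 10.3 gives no longitudinal method. What stands is that the two sources cannot be told apart with the data listed.
- *Within-season change.* It is tempting to treat the change from Day 0 to the post-dose sample as due to the vaccine alone. Section 2.1 argues against this, because the prior repertoire shapes the response.
- *Difference by vaccine sequence.* Section 2.1 says that LAIV is more efficacious than IIV in children, so infection could differ between Groups A and D. The switch of Group D to LAIV4 at age two limits this, and the groups also differ in age and are not randomized (5.3.1). No firm claim can rest on it.
- *Naivety.* Section 2.2 allows for children who are almost naive, so strict naivety is not claimed.
- *Stakes.* The study is exploratory (10.1), and 3.1 lists evolution as secondary. That limits the consequence but does not remove it: the study is meant to supply initial estimates for later designs, and those would carry the ambiguity forward.

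**Conclusion.** The concern holds in a limited form. For Groups A and D, no listed step specifically asks about influenza illness between one season's last visit and the next Day 0, and 10.3 does not account for it. Year-to-year repertoire change after repeated vaccination therefore cannot be separated from change due to natural infection.

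At an assumed risk of 10% to 30% per season, 0.6 to 1.8 of six children are infected in one interval, and 2.1 to 4.6 of six at least once over the maximum of four. Shorter follow-up gives fewer: 1.1 to 3.1 of six over two intervals. These figures rest on the assumed risk and, for repeated intervals, on independence across years. The conclusion that the sources cannot be separated does not depend on the exact rate, although its practical weight does.

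The matter is one of interpretation. No formal test or error rate is affected. It is worth acting on because the history is cheap to collect now and hard to recover reliably later.

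**What to change.** **Section 7.2.** At Day 0 for the young-child groups that give blood (A, B, D and E), add a parent-interview item on diagnosed or test-positive influenza and on influenza antiviral use: ever, at entry; since the last visit, at each annual return in Groups A and D.

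**Section 10.3.** Add that:
- between-season change (last sample of one season to the next Day 0) is reported as reflecting vaccine plus natural exposure;
- the evolution analysis is run with all children, and again leaving out each child with a reported infection from that interval onward, because infection may also alter later within-season responses;
- unreported or subclinical infection cannot be excluded.

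**Cost.** One interview item covering two recall periods, and a few sentences of analysis text. No added visit, sample or staff is needed.

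**Downside.** Parental report misses mild infections, so the item recovers only part of the infections counted above, and the documents do not allow that part to be estimated. The sensitivity set also shrinks. If every infection were reported, the children remaining after four intervals would be 6 x 0.9^4 = 3.9 at 10% risk and 6 x 0.7^4 = 1.4 at 30%. The second analysis is therefore descriptive, best shown as individual trajectories.
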